6.4 Online Surveys

Survey administration format will take place on Qualtrics FedRAMP electronic survey software accessed via the VA cloud OR the VA mPRO (mobile Patient-Reported Outcomes) mobile application. This will support data collection during the COVID 19 pandemic. Social distance guidelines and pandemic related challenges have made routine paper survey mailings unreliable. Participants can complete surveys over-the-phone with study staff if they prefer. Paper versions will also be available, if requested.

Qualtrics FedRAMP has been approved for use from the VA OIT Security standpoint (Authority to Operate or ATO). The ATO status is currently approved for 1 year and a full 3-year ATO is in the works. Qualtrics FedRAMP surveys will contain a study ID number, time of data entry and limited individually identifiable information. Within the VA firewall, the study team at the VA will create a custom-built tracking app that will track each participant's enrollment and study status. Data will be routinely extracted from Qualtrics FedRAMP in the VA cloud and stored on secure CCDOR servers, using SQL database connections. All data will be stored and utilized within secure CCDOR servers that are part of the Minneapolis VAMC network and which operate behind the VA firewall. All data is tracked using a SQL database, with a GUI-front end system that restricts access to only those with approval to study data.

Participants will be sent Qualtrics surveys via a generic email to their personal email address, if the patient opts in for email usage. Prior to emailing participants, we will contact them by phone to ask permission to use their email for this purpose. If the participant does not opt in for email usage, they will be given the Qualtrics survey URL verbally over-the-phone or written on the recruitment and/or follow-up letters sent to them in the mail. All emails to participants will be extremely generic and will follow VA guidelines; they will not mention details of the study in the body of the email, participant names and PHI will not be used. For emailed survey links, we will use CCDOR's well-established modified-Dillman protocol with repeated mailings and an incentive to boost response rates (see example of Dillman protocol chart below).

mPRO. The mPRO mobile app is designed to deliver research and quality improvement surveys to Veterans and their family members. The app allows VA researchers to select and create assessments and assign them to participants using fully deidentified invite codes. Participants then use their invite codes to sign into the mPRO mobile app.

To manage the risk of app-related information being intercepted by a third party, the following steps will be taken. First, the mPRO app will not be used (cannot be used) to collect any personally-identifying information and does not contain any open text fields that would allow a user to enter personally-identifying information. Second, any app usage data that is transmitted from a participant's phone to the research team will be linked only with a non-identifying subject identification code. In order to mitigate privacy risks that are inherent to using mobile phones or websites, we will be implementing several strategies. Participants will receive a unique invitation code that can be used to download and unlock the mPRO study app, and this unique code will be used to examine patient-reported outcomes. App usage data will be fully de-identified.

Qualtrics FedRAMP and mPRO surveys will contain minimal individually identifying information. The only identifying information will be information that is self-reported by the participants (e.g. name, phone, email, which is best method of contact). No sensitive data will be stored outside of the VA protected environment. Once data are transferred for data analysis, data will be maintained on password-protected VA computers in the VA environment and on secure VA servers. Study staff will monitor the functioning of the Qualtrics FedRAMP and mPRO applications. Only staff affiliated with this research protocol will have access to Qualtrics FedRAMP and mPRO data collected for this study. The PI or her designee will be responsible for monitoring data storage location and transfer of data between the VA cloud and VA server.

Study providers will also use email to contact participants using Mpls VA approved email protocol when patients opt in for personal email usage.

Table 1. Multi-modal follow-up protocol for baseline surveys for both Veterans and LOs.			
Day	A) US Postal Mail	B) Email Contact	C) Phone Contact
1: Recruitment Package	Delivery of info sheet, opt-out, Letter 1 (B1.V.L or B1.L.O.L)		
2: Day 0 – Phone screening (participant opts in or out of email usage)	Give participant personal code after consent; tell them to use URL from recruit letter.	Email (B2.V.E or B2.L.O.E) with link to survey after email address and consent is obtained	Call participant, discuss study using script (see study materials), obtain consent, screening, obtain verbal permission to send emails, provide link to survey and pin verbally.
3: Day 3		First email reminder with survey link to non-responders (B3.E.)	
4: Day 7		Second email reminder with survey link to non-responders (B4.E.)	First weekly outreach call to non-responders. Provide link to survey and pin verbally. (no script)
5: Day 14			Second weekly outreach call to non-responders. Provide link to survey and pin verbally. (no script)
6: Day 21		Third and final reminder email with survey link to non-responders (B6.E.)	Third weekly outreach call to non-responders. Provide link to survey and pin verbally. (no script)
*Day of survey completion			Thank you phone call and schedule assessment when applicable (veterans only)

Table 2. Multi-modal protocol for monthly surveys for both Veterans and LOs.			
Day	A) US Postal Mail	B) Email Contact	C) Phone Contact

1: Day 0		Email (M1.E) with link to monthly survey.	Call participant to inform them of fup survey; inform them of survey link email OR provide link to survey and pin verbally.
2: Day 3		First email reminder with monthly survey link to non-responders (M2.E.)	
3: Day 7		Second email reminder with monthly survey link to non-responders (M3.E.)	First weekly outreach call to non-responders. Inform them of survey link email OR provide link to survey and pin verbally. (no script)
4: Day 14			Second weekly outreach call to non-responders. Inform them of survey link email OR provide link to survey and pin verbally. (no script)
5: Day 21		Third and final reminder email with monthly 1 survey link to non-responders (M5.E.)	Third weekly outreach call to non-responders. Inform them of survey link email OR provide link to survey and pin verbally. (no script)

Table 3. Multi-modal follow-up protocol for fup surveys for both Veterans and LOs.

Day	D) US Postal Mail	E) Email Contact	F) Phone Contact
1: Prenotice	Fup prenotice letter to dropout dyads only (FU1.V.L or FU1.L.O.L)	Fup prenotice emails to dropout dyads only (FU1.V.E or FU1.L.O.E)	
2: Day 0		Email (FU2.V.E or FU2.SP.E) with link to fup 1 survey.	Call participant to inform them of fup survey; inform them of survey link email OR provide link to survey and pin verbally.
3: Day 3		First email reminder with fup survey link to non-responders (FU3.E.)	
4: Day 7		Second email reminder with fup survey link to non-responders (FU4.E.)	First weekly outreach call to non-responders. Inform them of survey link email OR provide link to survey and pin verbally. (no script)
5: Day 14			Second weekly outreach call to non-responders. Inform them of survey link email OR provide link to survey and pin verbally. (no script)
6: Day 21		Third and final reminder email with fup 1 survey link to non-responders (FU6.E.)	Third weekly outreach call to non-responders. Inform them of survey link email OR provide link to survey and pin verbally. (no script)

Table 4. Multi-modal follow-up protocol for 3M fup surveys for both Veterans and LOs.

--	--

Day	D) US Postal Mail	E) Email Contact	F) Phone Contact
1: Prenotice		3M fup prenotice emails (3M1.E)	
2: Day 0		Email (3M2.E) with link to 3M fup 1 survey.	Call participant to inform them of 3M fup survey; inform them of survey link email OR provide link to survey and pin verbally.
3: Day 3		First email reminder with 3M fup survey link to non-responders (3M3.E.)	
4: Day 7		Second email reminder with 3M fup survey link to non-responders (3M4.E.)	First weekly outreach call to non-responders. Inform them of survey link email OR provide link to survey and pin verbally. (no script)
5: Day 14			Second weekly outreach call to non-responders. Inform them of survey link email OR provide link to survey and pin verbally. (no script)
6: Day 21		Third and final reminder email with 3M fup 1 survey link to non-responders (3M6.E.)	Third weekly outreach call to non-responders. Inform them of survey link email OR provide link to survey and pin verbally. (no script)

7.0 Data Analysis

7.1 Qualitative Data Analysis.

We will utilize an efficient, rapid turn-around analytic approach well-suited to short-term projects, interviews that use targeted guides, and projects that lend themselves to straightforward explanatory analyses.⁶⁴ This approach uses data reduction, rather than coding, as the first step of analysis. Qualitative interviews will be transcribed verbatim. Following transcription of the first three interviews, [name] (with feedback from co-investigators) will develop a draft template that will be used to summarize each transcript. The template will include sections for each main topic of inquiry, unexpected findings, and exemplary quotes. After fielding the template and making any necessary revisions, [name] and the project manager (trained by [name]) will carry out the data reduction process. After all transcripts have been summarized, the project manager will transfer the summary points to a data matrix that organizes the summary points along each of our domains (acceptability, feasibility, and outcomes). Finally, following discussion of the matrix with the investigator team, [name] will create a memorandum summarizing findings and key themes.

7.2 Quantitative Data Analysis.

To evaluate acceptability of COACH, we will calculate the percentage of participants who report neutral or better treatment credibility and expectancy on the Credibility-Expectancy scale (CES)⁵⁶ and examine the distribution of scores on the Client Satisfaction Scale (CSQ-8).⁵⁷ To assess feasibility, descriptive statistics and graphical representations depicting intervention

fidelity, screening, and treatment retention will be generated. We will calculate rates of survey non-response and item missingness for assessment feasibility. To preliminarily evaluate outcomes, we will calculate and graphically display the direction and magnitude of change from baseline to follow-up for outcomes outlined in Table 1. We will also calculate the percentage of participants who improved, worsened, and experienced no change for each of these measures. We will calculate descriptive statistics and pre-to-post treatment effect sizes. Lastly, we will triangulate our quantitative data with qualitative themes through matrices with exemplary quotations. Themes that emerge from the interviews will be stratified by participants' scores on relevant quantitative scales (e.g., participants' acceptability themes stratified by their Credibility-Expectancy and Satisfaction scores; feasibility themes stratified by number of sessions attended).

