Background. PTSD occurs in as many as 17% of US military veterans and is associated with a host of negative, long-term consequences to the individual, their families, and society at large. EBPs, such as PE, result in clinically significant symptom relief for many. Yet, these therapies have proven less effective for military personnel and veterans and treatment dropout rates are high. Our team surveyed veterans initiating EBPs for PTSD and a family member across four VA medical centers (N = 598; Project HomeFront). We found that veterans were more than twice as likely to complete EBPs when loved ones encouraged them to confront distress and that veterans experienced greater treatment gains when they shared more with their loved ones about their treatment. A couples-based, exposure therapy for PTSD that integrates loved ones into every session of PE could provide the opportunity to mobilize the whole household in the service of EBP engagement, while extending the goals of therapy beyond symptom reduction to family functioning. We anticipate this intervention will teach couples to embrace a lifestyle that supports confronting trauma-related distress, so the veteran and his/her family can achieve optimal functional outcomes.

Objectives. We will complete stages 1A and 1B of the Stage Model of Treatment Development. Specifically, we will: (1) Expand our treatment outline using content experts and feedback from key stakeholders (veterans, loved ones, providers, and VA mental health leadership). (2) Conduct a pilot open trial to assess (a) the acceptability of treatment components, structure, and materials, (b) the feasibility of the intervention (retention and intervention fidelity), and (c) the study approach (screening, recruitment, and assessment process). (3) Explore the preliminary effects of the intervention on select outcomes including overall functioning, mental health functioning, social functioning, family functioning, and potential mechanisms (social control, subjective norms, and the degree to which veterans rely on their partners for support).

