2.0 Introduction

PTSD is a prevalent and potentially debilitating condition associated with a host of negative, long-term consequences and functional impairment.^{2,3,5,6,28} In response, the VA has made two EBPs widely available, PE and CPT. The evidence for the effectiveness of these therapies is

strong.⁸ In randomized controlled trials, these and other trauma-focused EBPs yield large symptom improvements, and most patients recover or improve²⁹. However, residual symptoms are common,²⁹ treatment response for military personnel lags behind other populations,¹² and dropout rates are high.³⁰ For example, among a large sample of post-9/11 veterans who initiated PE or CPT with a VA clinic over a 15-year period, 60% failed to complete an adequate dose of treatment.³⁰ PE and CPT are intensive treatments that require weekly, sustained attendance (10-12 weeks) and frequent, ideally daily, practice of the skills learned. In PE, this home practice is designed to break destructive habits of avoidance through repeated and sustained revisiting of traumatic memories (imaginal exposure) and approach of avoided activities in real life (*in vivo* exposure). Greater engagement in these activities predicts a two-fold increase in the odds of patients achieving good end state functioning and remission.¹⁴ However, patient engagement in these activities can be poor.¹³ Among HomeFront veterans who *completed* PE or CPT, only 38.7% finished most of their homework, and an important minority (20.3%) finished 25% or less of these assignments. Efforts to optimize the quality of veteran engagement in PE may hold promise as a pathway for maximizing the gains a given patient can reach.

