5.6 Human Subjects

For all research activities involving human subjects, we will obtain approvals from the VA's Central Institutional Review Board (IRB) with local approvals from the Minneapolis VA as required through the Central IRB process.

Table 1. Abbreviated Measures (see Materials document for exhaustive list of measures and items)

Domain	Reporter		Source			Measure
	V	LO	S	I	A	
Acceptability						
Treatment Structure	X	X	X	X		CES ⁵⁶ ; CSQ-8 ⁵⁷
Materials	X	X		X		N/A
Feasibility						
Treatment Retention	X	X	X	X	N/A	

Treatment Fidelity		X	Fidelity instrument ^b
Screening Approach		X	N/A
Recruitment Approach		X	N/A
Assessment Process	X X	X X	All survey measures
Outcomes: Functioning			
Overall functioning	X X	X	Short Form Survey ⁵⁸
MH functioning	X X	X X	CAPS ⁵² , PCL-5 ⁵⁹ ; PHQ-9 ^{,60}
Self-care functioning	X X	X	IPF ⁵⁵
Family functioning	X X	X	IPF ⁵⁵
Romantic functioning	X X	X	IPF ⁵⁵
Communication	X X	X	Prepare/Enrich ⁶¹
Conflict Resolution	X X	X	Prepare/Enrich ⁶¹
Parenting	X X	X	IPF ⁵⁵
Social functioning	X X	X	IPF ⁵⁵
Outcomes: Mechanisms			
Session Attendance		X	N/A
HW Compliance		X	PEAS ⁶²
Social control	X X	X	Emotional and Problematic Support ⁶³
Subjective Norms	X X	X	Subjective Norms-PTSD ^a
LO Reliance	X X	X	Treatment Discussions ^a

^aUnpublished scale from Project HomeFront. ^bDeveloped during the study
 V = Veteran; LO = Loved One; A = Administrative data; S = Survey; I = Interview.

severe relationship violence in the past year. We will exclude veterans who are typically excluded from trauma-focused treatment due to counter-indications, including (1) severe substance use, (2) uncontrolled psychosis or mania, and (3) active suicidal or homicidal ideation, which should be the focus of clinical attention. Lastly, (4) we will exclude dyads in which the loved one also screens positive for PTSD. See below for exhaustive list of inclusions/exclusions.

A.2. Data Sources

Data sources will include surveys, semi-structured qualitative interviews, and administrative data. Veterans and their LOs will complete surveys prior to treatment (baseline), during treatment, after their final COACH session, and 3-months after their final COACH session. Those who do not attend their final session will receive their survey by mail or email (Qualtrics link) using CCDOR's modified-Dillman protocol.⁵⁴

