6.0 Data Collection & Study Evaluations

6.1 Data Collection.

Data collected will include surveys, semi-structured qualitative interviews, and administrative data. The outcomes of interest for Aims 2 & 3 (acceptability, feasibility, functioning, and mechanisms), their source, and the specific measure (as applicable) are presented in Table 1. Couples will complete surveys prior to treatment (baseline), during treatment, and within four weeks of their final COACH session. Those who do not attend their final session will receive their survey by mail using CCDOR's modified-Dillman protocol.⁵⁴

Consistent with recommendations, we will obtain collateral reports on veteran functioning by asking LOs to report on the veterans' functioning on the Inventory of Psychological Functioning (IPF).⁵⁵ Veterans will also complete a posttreatment structured clinical interview for PTSD symptoms.⁵² Lastly, veterans and LOs will complete 90-minute semi-structured qualitative exit interviews.

All interviews will be conducted in person or by phone, based on the interviewee's preference, and will be audio-recorded. Qualitative exit interviews (Appendix 2) will assess (1) attitudes about intervention components, structure (e.g., level of therapist contact), and materials (e.g., handouts), (2) acceptability and efficacy of COACH, including suggestions for intervention improvement, (3) engagement with COACH, including retention and barriers/facilitators to

Table 1. Select Measures. See materials document for full list.

Domain	Reporter		Source			Measure
	V	LO	S	I	A	
Acceptability						
Treatment Structure	X	X	X	X		CES ⁵⁶ ; CSQ-8 ⁵⁷
Materials	X	X		X		N/A
Feasibility						
Treatment Retention	X	X		X	X	N/A
Treatment Fidelity				X		Fidelity instrument ^b
Screening Approach				X		N/A
Recruitment Approach				X		N/A
Assessment Process	X	X	X	X		All survey measures
Outcomes: Functioning						
Overall functioning	X	X	X			Short Form Survey ⁵⁸
MH functioning	X	X	X	X		CAPS-5 ⁵² , PCL-5 ⁵⁹ , PHQ-9 ⁶⁰
Self-care functioning	X	X	X			IPF ⁵⁵
Family functioning	X	X	X			IPF ⁵⁵
Romantic functioning	X	X	X			IPF ⁵⁵
Communication	X	X	X			Prepare/Enrich ⁶¹
Conflict Resolution	X	X	X			Prepare/Enrich ⁶¹
Parenting	X	X	X			IPF ⁵⁵
Social functioning	X	X	X			IPF ⁵⁵
Outcomes: Mechanisms						
Session Attendance				X		N/A
HW Compliance				X		PEAS ⁶²
Social control	X	X	X			Emotional and Problematic Support ⁶³
Subjective Norms	X	X	X			Subjective Norms-PTSD ^a
LO Reliance	X	X	X			Treatment Discussions ^a

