^aUnpublished scale from Project HomeFront. ^bDeveloped during the study
V = Veteran; LO = Loved One; S = Survey; I = Interview; A = Administrative Data.

engaging with the program, (4) perceptions of the impact of the program on the intervention targets (e.g., functioning, social control, subjective norms, and LO reliance) and exploration of unexpected domains impacted by the program, and (5) the completeness and time burden of the survey battery. We will also extract the following administrative data: (1) the number of sessions attended (from electronic medical record; retention), (2) the number of participants screened each month (screening), and (3) the number of eligible veterans and LOs who declined participation (recruitment),

and therapists' ratings of homework compliance using two items adapted from the Patient Exposure and Response Prevention Adherence Scale (PEAS) for Obsessive Compulsive Disorder (also a cognitive-behavioral exposure therapy).⁶²

6.2 Fidelity Checklists and Provider Training.

Over the course of the open trial, [name] will lead efforts to finalize fidelity checklists, and [name] will lead efforts to develop the provider training program. We anticipate the provider training program will follow a structure similar to that of the VA's national PE and ICBT trainings. These include an initial didactic training with role plays (PE is 4 days; ICBT is 2.5 days) followed by two training cases with individual feedback and weekly case consultation. Additional materials needed for the training program (e.g., powerpoint, clinical vignettes, role play exercises) will be included in the final RCT manual for COACH. Each therapy session will be recorded. We will apply the fidelity checklists to one randomly selected session for each couple. We will identify gaps in content covered by checklist items and items that are unclear, difficult to rate, or not consistently applicable. Items will be revised and finalized for the final Stage II Manual.²⁵

6.3 Final RCT Manual.

During the conduct of the open trial, Drs. [name] and [name] will meet weekly and the larger team will meet monthly to discuss new observations, successes, and challenges. They will identify

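### The planned assessment-feasibility rates cover surveys only, so they could not show loss of the posttreatment CAPS-5 or exit interview among couples who drop out

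*Combined protocol and SAP*

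**What the plan says.** Aim 2(c), in the Abstract and Section 3.0, is to assess "the study approach (screening, recruitment, and assessment process").

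Section 7.2 gives the quantitative measure for the assessment part: "We will calculate rates of survey non-response and item missingness for assessment feasibility". In the measures table (Table 1, Sections 5.6 and 6.1), the row for the assessment process marks both survey and interview as sources, but the measure named is "All survey measures". The exit-interview topic on assessment is "the completeness and time burden of the survey battery".

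The posttreatment battery is wider than the survey. Section 6.1 states "Veterans will also complete a posttreatment structured clinical interview for PTSD symptoms" and adds a 90-minute exit interview for veterans and loved ones. Neither is made conditional on finishing treatment, and all interviews may be held in person or by phone.

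For people who miss the last session, Section 6.1 says "Those who do not attend their final session will receive their survey by mail"; Section 5.6 (A.2) says "Those who do not attend their final session will receive their survey by mail or email". Section 6.4, Table 3 adds a prenotice for dropout dyads, again for the survey. No corresponding step is stated for either interview.

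**The concern.** This pilot exists to prepare a randomized trial. In Table 1 the CAPS-5 is the only interviewer-rated functioning outcome, so whether it can be collected from veterans who leave treatment is something the pilot should measure. The exit interview is meant to explain retention and barriers to engagement, and couples who left are the people best placed to do so.

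If both interviews were lost in dropouts, the two planned rates would not move, because neither counts interviews. An application for the next trial could then report good assessment feasibility on a basis that leaves out two of the three posttreatment assessments.

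**Working it through.** The plan has no figure to reproduce. It states no dropout allowance, no assessment-completion target and no feasibility threshold. The check is therefore a comparison of the provisions, followed by a count.

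**Provisions side by side**

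| | Survey | CAPS-5 (veterans) | Exit interview (both partners) |
|---|---|---|---|
| Planned at posttreatment | yes | yes | yes |
| Conditional on completing therapy | no | no | no |
| Phone possible | yes | yes | yes |
| Collection window stated | four weeks (6.1) | none stated | none stated |
| Contact step after a missed final session | yes (5.6, 6.1, 6.4 Table 3) | none stated | none stated |
| Quantitative feasibility measure in 7.2 | non-response, item missingness | none | none |

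Two details support the reading. The administrative data listed in Section 6.1 are session counts, monthly screening counts, refusals among the eligible, and therapist homework ratings; completed interviews are not among them. In Section 6.4, the call that schedules the diagnostic assessment appears in the baseline table (Table 1) and not in the posttreatment table (Table 3).

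**Illustrative count**

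Inputs: N = 12 veterans (Abstract, Sections 5.1 and 5.6A). Dropout d is assumed at 20%, 40% and 60%. The top of that range borrows the background statement in Section 2.0 that "60% failed to complete an adequate dose of treatment", which describes PE or CPT in VA care and not this trial. It is also assumed that every dropout returns the survey and misses the interviews.

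Dropouts k = N × d, rounded. CAPS-5 completion = (N − k)/N, with exact (Clopper-Pearson) 95% intervals. Exit interviews missing = 2k of 2N.

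| d | N × d | k | Survey non-response | CAPS-5 missing | CAPS-5 completed (95% CI) | Exit interviews missing |
|---|---|---|---|---|---|---|
| 20% | 2.4 | 2 | 0% | 2/12 = 16.7% | 10/12 = 83.3% (51.6 to 97.9) | 4/24 |
| 40% | 4.8 | 5 | 0% | 5/12 = 41.7% | 7/12 = 58.3% (27.7 to 84.8) | 10/24 |
| 60% | 7.2 | 7 | 0% | 7/12 = 58.3% | 5/12 = 41.7% (15.2 to 72.3) | 14/24 |

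Section 5.3A gives ten veterans instead of 12. With N = 10, CAPS-5 missing would be 2, 4 or 6 of 10.

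At least one dropout is likely across the range: with N = 12, 1 − 0.8^12 = 0.93 at 20% and 1 − 0.6^12 = 0.998 at 40%.

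**The case against.** The best case for the plan as it stands has five parts.

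- **The feasibility evidence is broader than one number.** Item missingness is planned as well as non-response, and the exit interview contributes qualitative evidence. This stands. A reader who inferred that feasibility rests on survey non-response alone would be wrong. All of this evidence still concerns the survey battery.
- **Dropouts are not excluded from the interviews.** Both are planned for all participants, without a completion condition and with a phone option. Table 3 sits under the heading on online surveys, so its silence on interviews is unsurprising, and the scripts are in a separate materials document. This also stands. A reader might infer that the interviews would come only from couples who finish; the documents do not say so. What is missing is a stated contact and timing step for dropouts.
- **Loss might show elsewhere.** Section 7.2 stratifies feasibility themes by sessions attended, so missing exit interviews could leave low-attendance strata thin. CAPS-5 loss could be read from the number behind the change scores, if that number is reported. Both are indirect, neither is a rate, and the second belongs to Aim 3.
- **Survey and interview loss may go together.** If dropouts missed both, survey non-response would rise. True, and 0% is the extreme case. Even then, the survey rate would not show how many interviews were obtained.
- **Symptom data on dropouts are still sought.** The PCL-5 is a survey measure and follows the survey's outreach route. This limits the damage to the symptom results but does not show whether the CAPS-5 is feasible.

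It is also fair that no hypothesis test or go/no-go rule depends on the missing percentage.

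**Conclusion.** The gap is real and modest. The assessment process under Aim 2(c) includes two posttreatment interviews for which Section 7.2 plans no completion rate and for which no dropout contact step is stated. The planned rates could not reveal their loss among dropouts. This follows from the text and needs no assumption.

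The size is illustrative only: 2 to 7 of 12 veterans without a CAPS-5, given 20% to 60% dropout and loss of the interview in every dropout, while survey non-response could still read 0%. Both conditions are assumptions.

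A reader might go further and infer a bias of known size in the CAPS-5 change. The documents give no CAPS-5 change for completers or dropouts, so no such figure can be supported.

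Because the study is descriptive and has no feasibility threshold, this is a worthwhile, inexpensive improvement to reporting and follow-up. It does not invalidate the design.

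**What to change.** 1. **Section 7.2.** Report completion of the posttreatment CAPS-5 (veterans) and of the exit interview (veterans and loved ones, separately) beside survey non-response. Use all couples who began COACH as the denominator and split by final-session attendance. Count those who withdrew from the study (Section 7.3) as not completed, and show them separately from those who only stopped therapy.
2. **Section 6.1 and Section 6.4, Table 3.** Add an offer to schedule both interviews by phone for couples who stop therapy but have not withdrawn from the study, with a stated window.
3. **Sample size.** Reconcile ten (Section 5.3A) with 12 (Abstract, Sections 5.1 and 5.6A), since enrolment limits the denominator of these rates.

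The cost is protocol wording, two additional completion measures and some extra calls. The interviews and their $60 payments (Section 5.8D) are already planned for participants. The drawback is that the completion figure may look less favourable than the survey rate alone.

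### Does section 7.2 leave session attendance, homework compliance and the monthly survey scores without a workable analysis?

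*Combined protocol and SAP*

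**What the plan says.** Section 7.2 sets the outcome analysis in three steps. First, "we will calculate and graphically display the direction and magnitude of change from baseline to follow-up for outcomes outlined in Table 1". Second, it will report "the percentage of participants who improved, worsened, and experienced no change for each of these measures". Third, "We will calculate descriptive statistics and pre-to-post treatment effect sizes". The same section promises descriptive statistics and graphs for treatment retention, rates of survey non-response and item missingness, and a cross-tabulation of interview themes with quantitative data, including "feasibility themes stratified by number of sessions attended".

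Table 1 in section 6.1 has a block headed "Outcomes: Mechanisms" with five rows: session attendance, homework compliance, social control, subjective norms and reliance on the loved one. The text of 6.1 gives the source of the first two. Attendance is "the number of sessions attended (from electronic medical record; retention" by label, and homework is captured by "therapists' ratings of homework compliance using two items adapted from the Patient Exposure and Response Prevention Adherence Scale".

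Sections 5.6C and 5.8D say that both partners fill in monthly surveys of outcomes and mechanisms, each paid at $25. Table 2 in section 6.4 gives the contact schedule for them.

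**The concern.** Two things look wrong on a first reading. The change rule is worded to cover every outcome in Table 1. Attendance and homework ratings exist only once therapy has started, and section 6.1 places baseline before treatment. For these two rows there is nothing to subtract from, and a participant cannot be classed as improved or worsened.

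The second point is the monthly surveys. Both members of each couple complete them, with reminders and payment, and they cover the mechanisms that the therapy is meant to move. The outcome analysis in 7.2 speaks only of baseline, follow-up, pre and post. If the monthly scores were never looked at, the time course of social control, subjective norms and reliance on the partner would go unreported, and participants' effort would have served only to measure response rates. The form of the homework summary would also be chosen after the data were seen.

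**Working it through.** **Which outcomes cannot follow the rule.** Table 1 in section 6.1 has 9 functioning rows (overall, mental health, self-care, family, romantic, communication, conflict resolution, parenting, social) and 5 mechanism rows, so 9 + 5 = 14. Two have no pre-treatment value: 2/14 = 14%. Neither is one of the three mechanisms named in Aim 3 (section 3.0), and all three of those are survey scales to which pre-post change can be applied.

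**What 7.2 already provides for those two rows.**

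| Row | Change rule | Other cover in 7.2 |
|---|---|---|
| Session attendance | Cannot be run | Retention descriptives and graphs; feasibility themes stratified by sessions attended |
| Homework compliance | Cannot be run | General descriptive statistics |

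Section 6.1 itself labels the session count as retention, so the retention summary is the attendance summary. That leaves one row, a two-item rating, without a summary of its own.

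**How many monthly surveys are at issue.** No count is stated, but the payment totals in 5.8D imply one. Let *m* be the number of monthly surveys per person.

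- Veterans: 40 + 50 + 60 + 60 + 60 + 70 = 340. Setting 340 + 25*m* = 415 gives *m* = 75/25 = 3.
- Loved ones: 40 + 60 + 60 + 70 = 230. Setting 230 + 25*m* = 305 gives *m* = 75/25 = 3.

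Both stated totals are reproduced with *m* = 3. This fits the usual treatment length in 5.2A: 13 weekly sessions are 91 days, and 91/30.4 = 3.0 months; 15 sessions are 105 days, and 105/30.4 = 3.5 months. Length is flexible, so 3 is an inferred maximum. With 12 couples (section 5.6A) that is 12 × 2 × 3 = 72 surveys; with ten (section 5.3A) it is 10 × 2 × 3 = 60.

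**What 7.2 provides for those surveys.** Non-response and missingness rates serve Aim 2(c), the assessment process, for which Table 1 names all survey measures. The promise of descriptive statistics is not limited to two time points. A graph of change from baseline to follow-up fixes where the display starts and ends; it does not exclude the points in between.

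**What Aim 3 needs.** It asks for an exploration of preliminary effects on the listed outcomes and mechanisms. It does not ask for trajectories, mediation or temporal ordering. Section 5.4 describes the study as pre-post and lists that as a limitation. The planned analysis therefore matches both the aim and the design. The exit interviews add a qualitative view, covering "perceptions of the impact of the program on the intervention targets (e.g., functioning, social control, subjective norms, and LO reliance" and related topics.

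**The case for a change.** The best case for a change rests on homework. Section 2.1 puts at-home practice on the causal path: shifting the three mechanisms should raise the amount and quality of practice, which should reduce symptoms. Section 2.0 reports that only 38.7% of veterans who completed therapy in the earlier survey study finished most of their homework. A measure so central to the rationale deserves a stated summary. The monthly surveys likewise observe the mechanisms while they should be operating, which neither a pre-post contrast nor a recollection at exit interview can do. A few sentences would settle both points before results are seen, with no new data collection.

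Some of this stands. The change rule is worded more broadly than it can be applied, homework compliance is not named in 7.2, and no display of the monthly scores is specified. It does not follow that the analysis would go wrong. A level or distribution over the course of treatment is the natural summary of a two-item rating in 10 to 12 couples, and it falls within the descriptive statistics already promised. With no hypothesis test, comparator or success threshold, the choice of display leaves no formal inference open to bias. Plotting every wave would be a useful extra, but it is a preference. Which scales are given monthly is set out in a separate materials document, so a more detailed display plan could not be checked against the text available here.

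**Conclusion.** No change is needed. The literal reading fails for 2 of 14 outcome rows, and attendance, one of the two, already has its own summary in 7.2. The residue is the unspecified form of a homework summary and the unspecified display of at most 60 to 72 monthly surveys. Analysts can fill both gaps sensibly under the descriptive statistics that 7.2 promises, and neither affects pre-post change in the three mechanisms of Aim 3. Limiting change scores to measures with a baseline would only write down what any analyst would do.

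This rests on three assumptions: that the general descriptive statistics are read as covering all collected outcome data; that the monthly count inferred from the payment totals is about right; and that the pilot stays descriptive. If these measures were later used in a formal mediation analysis or a progression rule, the analysis would need to be specified in advance.
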